9.5.5.2 Unsolicited Adverse Event

An unsolicited local and general AE or symptoms are the one whose nature or intensity is NOT consistent with the expected AEs described and listed above in this protocol. Information of unsolicited symptoms/AEs will be collected during study period and reported at each visit or safety calls.

9.5.5.3 Time Period and Frequency for Collecting AE and SAE Information

The time period for actively eliciting and collecting AEs and SAEs (“active collection period”) for each participant begins from the time the participant receiving vaccination. All AEs, including AESI, MAAE and SAE, will be collected during the study period.

Follow-up by the investigator continues throughout and after the active collection period and until the AE or SAE or its sequelae resolves or stabilizes at a level acceptable to the investigator.

If the participant withdraws from the study and also withdraws consent for the collection of future information, the active collection period ends when consent is withdrawn.

If a participant definitively discontinues or temporarily discontinues study intervention because of an AE or SAE, the AE or SAE must be recorded on the CRF and the SAE reported using the SAE reporting form.

9.5.6 Adverse events (AEs)

9.5.6.1 Definition of Adverse Events (AE)

An AE is any untoward medical occurrence in a patient or clinical investigation subject temporally associated with the use of a medicinal product, whether or not considered related to the medicinal product. The occurrence does not necessarily have to have a causal relationship with this treatment. An AE can therefore be any unfavorable and unintended sign (including an abnormal laboratory finding), symptom, or disease (new or exacerbated) temporally associated with the use of a medicinal product, whether or not considered related to the medicinal product.

Examples of an AE include:

- Exacerbation of a chronic or intermittent pre-existing condition, including either an increase in frequency and/or intensity of the condition
- **A new condition detected or diagnosed, even though it may have been present prior to this**
- Signs, symptoms, or the clinical sequelae of a suspected interaction
- Signs, symptoms, or the clinical sequelae of a suspected overdose of either study drug or a concurrent medication.

Examples of an AE do NOT include:

- A medical or surgical procedure (*e.g.* endoscopy); the condition that leads to the procedure is an AE
- Situations where an untoward medical occurrence did not occur (social and/or convenience admission to hospital)
- Anticipated day-to-day fluctuations of pre-existing disease(s) or condition(s) present or detected before informed consent is obtained, that do not worsen.

A priori, immunogenicity endpoints as specified in the protocol will not be considered as AEs except if, because of the course or severity or any other features of such events, the investigator, according to his/her best medical judgment, considers these events as exceptional in this medical condition.

9.5.6.2 Definition of Serious Adverse Events (SAE)

A SAE is any untoward medical occurrence that at any dose:

- Results in death or,
- Is life-threatening or,

Note: The term "life-threatening" in the definition of "serious" refers to an event in which the subject was at risk of death at the time of the event; it does not refer to an event, which hypothetically might have caused death if it were more severe.

- Requires inpatient hospitalization or prolongation of existing hospitalization or,

Note: In general, hospitalization signifies that the subject has been detained (usually involving at least an overnight stay) at the hospital or emergency ward for observation and/or treatment that would not have been appropriate in the physician's office or out-subject setting. Complications that occur during hospitalization are AEs. If a complication prolongs

hospitalization or fulfils any other serious criteria, the event is serious. When in doubt as to whether hospitalization occurred or was necessary, the AE should be considered serious. Hospitalization for elective treatment of a pre-existing condition that did not worsen from baseline is not considered an AE.

- Results in persistent or significant disability/incapacity or,

Note: The term disability means a substantial disruption of a person's ability to conduct normal life functions. This definition is not intended to include experiences of relatively minor medical significance such as uncomplicated headache, nausea, vomiting, diarrhoea, influenza, and accidental trauma (e.g. sprained ankle), which may interfere or prevent everyday life functions but do not constitute a substantial disruption.

- Is a congenital anomaly/birth defect or,
- Is a medically important event

Note: Medical and scientific judgment should be exercised in deciding whether expedited reporting is appropriate in other situations, such as important medical events that may not be immediately life threatening or result in death or hospitalization but may jeopardize the subject or may require intervention to prevent one of the other outcomes listed in the definition above. These should also be considered serious. Examples of such events are invasive or malignant cancers, intensive treatment in an emergency room or at home for allergic bronchospasm, blood dyscrasias or convulsions that do not result in hospitalisation, or development of drug dependency or drug abuse.

An AE fulfilling any one or more of these criteria should be reported as a SAE, irrespective of the dose of drug given, and even if it is the result of an interaction or drug abuse.

A distinction should be drawn between serious and severe AEs. The term 'severe' is often used to describe the intensity (severity) of a specific event (as in mild, moderate, or severe myocardial infarction); the event itself, however, may be of relatively minor medical significance (such as severe headache). This is not the same as 'serious,' which is based on subject's event outcome or action criteria usually associated with events that pose a threat to a subject's life or functioning. The seriousness (not severity) serves as a guide for defining regulatory reporting obligations.

9.5.6.3 Definition of Unexpected Adverse Reaction Definition

An unexpected adverse reaction is any untoward and unintended response that is related to the administration of the study agent, at any dose that is not consistent with the applicable product information (e.g., current version of the Investigator's Brochure for an unauthorized investigational medicinal product or summary of product characteristics for an authorized product).

9.5.6.4 Definition of Medically Attended Adverse Event

A Medically Attended Adverse Event (MAAE) is an AE with a medically-attended visit that is not a routine visit for physical examination or vaccination, such as visits for hospitalization, an emergency room visit, or an otherwise unscheduled visit to or from medical personnel (medical doctor) for any reason.

9.5.6.5 Definition of Adverse Events of Special Interest (AESI)

Adverse event of special interest (AESI) is further defined in Council for International Organizations of Medical Sciences (CIOMS) VII as [15]:

An adverse event of special interest (serious or non-serious) is one of scientific and medical concern specific to the sponsor's product or specific target disease, for which ongoing monitoring and rapid communication by the investigator to the sponsor could be appropriate. Such an event might require further investigation in order to characterize and understand it. Depending on the nature of the event, rapid communication by the trial sponsor to other parties (e.g., regulators) might also be warranted. Thus AESI should include potential immune medical condition (listed in **Table 9-6**), or any newly identified potential AESI followed through 12 months after participants' final vaccination. Complications of COVID-19 (listed in **Table 9-5**) should be considered and reported as AESIs.

Subjects will be assessed for diagnosis of an AESI at all visit. AESIs include potential ADE medical conditions, AE specific to complications of COVID-19, or other potential AEs that may be determined at any time by regulatory authorities as additional information concerning COVID-19 is obtained. Given the concern for "cytokine storm", an AESI of cytokine release syndrome will be included as an AE specific to COVID-19. Thus AESI included

AESIs specific to complications of potential disease enhancement for COVID-19, also termed ADE (antibody dependent enhancement), will also be monitored (see **Table 9-5**).

Table 9-5 Adverse Events of Special Interest Relevant to COVID-19^a

Body System	Diagnoses ^a
Immunologic	Enhanced disease following immunisation, ^b cytokine release syndrome related to COVID-19 ^c , Multisystem inflammatory syndrome in children (MIS-C)
Respiratory	Acute respiratory distress syndrome (ARDS)
Cardiac	Acute cardiac injury including: 
 • Microangiopathy • Heart failure and cardiogenic shock • Stress cardiomyopathy • Coronary artery disease • Arrhythmia • Myocarditis, pericarditis
Hematologic	Coagulation disorder 
 • Deep vein thrombosis • Pulmonary embolus • Cerebrovascular stroke • Limb ischemia • Hemorrhagic disease • Thrombotic complications
Renal	Acute kidney injury
Gastrointestinal	Liver injury
Neurologic	Guillain-Barré Syndrome, anosmia, ageusia, meningoencephalitis

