6.2 Primary Endpoint(s)

Immunogenicity Endpoint(s)

- Geometric mean titer (GMT) of SARS-CoV-2 neutralizing antibody on Day 57
- Seroconversion rate (SCR) of SARS-CoV-2 neutralizing antibody on Day 57

Safety Endpoint(s)

- Local reactions for up to 7 days following each dose
- Systemic events for up to 7 days following each dose
- Unsolicited AEs from Day 1 to Day 57
- MAAEs and SAEs from Day 1 to Day 365
- AESIs and ADEs from Day 1 to Day 365

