It will be consisted of 7 clinical visits and one long-term follow-up visit. All subjects will have blood test for safety before and after full vaccination. Subjects in lot-to-lot consistency and immunogenicity group will also have blood drawn for immune response, in which tests for T cell function will be optional. Subjects will come to the clinics at Visit 1 for screening, Visit 2 (Day 1, baseline) for randomization and 1st vaccination, Visit 3 (Day 29) for 2nd vaccination, Visit 4 (Day 57) for safety check and immunogenicity assessment, and Visit 5 (Day 197) for safety check and assessment of the persistence of immune response. **Subjects will also be unblinded at Visit 5. Subjects in placebo group will withdraw from the study and subjects in vaccine group will be encouraged to have 3rd dose of vaccination at Visit 6 (Day 197~Day 242). Those who received 3rd dose will have Visit 7 (14 days after Visit 6) to check the booster effect. After Day 197, subjects will enter the long-term follow-up with a safety call bi-monthly.** Subjects in lot-to-lot and immunogenicity group will be encouraged to visit site at Day 365 to check the immune persistence. Thus, subjects will be expected to participate for up to a maximum of approximately 13 months. Unblinding will be carried out when **subjects** in core group or supplementary group have completed Visit 5. For females of child-bearing potential, a urine pregnancy test will be performed before **each** vaccination and will be found negative. Female subjects or the female partners of male subjects who are pregnant during the study period will be followed the pregnancy outcomes.

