All subjects will come back on Day 197, Visit 5, for immunogenicity persistence check in immunogenicity group and safety check for safety group. **Once subject completes Visit 5, he or she will be unblinded. Subjects received placebo will withdraw from the study and subjects who received UB-612 vaccine will be invited to join the extension study to determine the durability of the immune response and long-term safety after unblinding. Meanwhile, subjects in vaccine group will be encouraged to have a third dose of UB-612. All subjects who received UB-612 vaccine will be followed up for 12 months.**

All subjects will receive safety calls on Day 8, Day 15, Day 22, Day 36, Day 43, Day 64, Day 71, Day 78, Day 85, Day 253, and Day 309 that will serve both to monitor for unsolicited AEs or/and to monitor for symptoms of COVID-19. After Day 57, each week (i.e., every 7 days) the subject will receive a prompt on their smartphone device to regularly surveillance for signs and symptoms of COVID-19 and SAE. **Subjects who received 3rd dose of UB-612 will receive an extra safety call on 7 days post 3rd vaccination.**

If a Grade 3 local reaction, systemic event, or fever are reported in the reactogenicity e-diary, a telephone contact should occur to ascertain further details and determine whether a site visit is clinically indicated. If suspected Grade 4 local reaction systemic event and /or fever is reported in the reactogenicity e-diary, a site visit should occur to confirm whether the event meets the criteria for Grade 4. All subjects were encouraged to contact site staff once they encountered Grade 3/4 AE. Allergic skin reaction should be monitored for 14 days post vaccination and should be contacted regardless of severity.

If a subject experiences a febrile illness associated with respiratory symptoms, he or she is instructed to contact the site immediately. Subjects may utilize a COVID-19 illness e-diary to prompt him/her to report any symptoms.

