b: Screening for pregnancy and proteinuria will be performed by urine sample on Day 1, Day 29. When positive urine pregnancy test is presented, it should be confirmed by a serum test. Serum testing in lieu of urine tests will not be considered a protocol deviation. Proteinuria is checked via urine routine as baseline.

c: For anti-S1-RBD IgG levels, SARS-CoV-2 neutralizing titers, and antibody titers which inhibit S1-RBD: ACE2 binding.

d: All subjects will receive safety calls that will serve both to monitor for unsolicited AEs, including AESIs, and to monitor for symptoms of COVID-19.

e: Each week (i.e., every 7 days) the subject will receive a prompt on their smartphone device to regularly surveillance for signs and symptoms of COVID-19. Record medication for potential COVID-19 on COVID-19 page.

f: Only record medications for MAAE and SAE.

g: 28 days after 2nd vaccination

h: **Only for subjects in vaccine group and have agreed to receive 3rd dose of UB-612.**

i: 12 months (336 days) after 2nd vaccination

j: Safety laboratory includes complete blood count (Hgb, Hct, RBC), WBC with differential, platelet count, creatinine, ALT, AST, total and direct bilirubin, hs-CRP, and ANA.

k: Active collection period

l: Passive surveillance period.

m: Visit 1 and 2 could be emerged as one visit.

n: Anti-S1-RBD IgG level only

o: Up to 100 aged >18-< 65 subjects in selected sites will be invited

p: To include PIMMC (listed in **Table 9-6**), or any newly identified potential AESI followed through 12 months after participants' final vaccination. Complications of COVID-19, also termed as ADE, (listed in **Table 9-5**) should be considered and reported as AESIs.

q: **If subject encountered \geq Grade 3 hypertension, the existence or deterioration of proteinuria will be checked .**

r: **An aliquot of spared serum is to be frozen and stored for UBI SARS-CoV-2 ELISA, Confirmatory SARS-CoV-2 ELISA, and future immunologic tests.**

s: **Subjects who qualified to receive 3rd dose will enter 2 weeks e-diary for follow-up and a safety call post 7 days post vaccination.**

t: **Visit 5 and Visit 6 could be the same day.**

u: **Approximately thirty aged >18-< 65 subjects and approximately thirty aged \geq 65 years subjects in selected sites will be invited. When applicable, subjects who were assessed for T cell functions on Day 57 are preferred to be invited.**

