8.1.9 Visit 6 (Day 197~242) –3rd Vaccination

The following procedures will only be performed on subjects who agreed to have 3rd vaccination. The Visit 5 and Visit 6 could be the same day.

- (1) Collect informed consent form for vaccine group who agreed to have 3rd vaccination.**
- (2) Check contraindication for the third vaccination and the possibility of delay vaccination**
- (3) Conduct physical examination.**
- (4) Measure vital signs.**
- (5) Perform a urine pregnancy test.**
- (6) If subject encountered \geq Grade 3 hypertension, subject should be checked the existence or deterioration of proteinuria or other renal damage sign.**
- (7) Collect blood sample for following tests:**
 - **Immune response assessments**
 - **Blood routine tests**
 - **Biochemistry test**
 - **Immunology test**
 - **T cell function (optional)**
- (8) Perform 3rd vaccination**
- (9) Observe closely during vaccination and at least 30 minutes after vaccine administration for the change of vital sign or acute anaphylactic event at site by site staff.**
- (10) Instruct the subject to monitor body temperature and complete self-evaluation e-diary correctly.**

(11) Review concomitant medications.

(12) Conduct COVID-19 surveillance

(13) Record and report adverse event, serious adverse event, or any symptoms of COVID-19 if any has occurred since the previous visit.

8.1.10 Safety call on 7 days after Visit 6 (Only for subjects who have 3rd vaccination)

Safety calls on 7 days after Visit 6 to monitor subjects' unsolicited AEs and symptoms of COVID-19. Call should be inquired the phenomenon of allergic skin reaction, especially itching and redness, or other unsolicited allergy reaction. No matter injection site or extending to other body site, site staff should arrange unscheduled visit to verify the allergic reaction and check HLA typing if indicated.

8.1.11 Follow up on 14 days after Visit 6 (\pm 3 day) (Only for subjects who have 3rd vaccination)

(1) Conduct physical examination.

(2) Measure vital signs.

(3) If subject encountered \geq Grade 3 hypertension, subject should be checked the existence or deterioration of proteinuria or other renal damage sign.

(4) Collect blood sample for following tests:

➤ **Immune response assessments**

➤ **Blood routine tests**

➤ **Biochemistry test**

➤ **Immunology test**

➤ **T cell function (optional)**

(5) Review concomitant medications.

(6) Conduct COVID-19 surveillance

(7) Record and report adverse or serious adverse event.

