8.1.13 Long-term follow-up (Day 365 \pm 45 days)

(1) Measure vital signs.

(2) If subject encountered \geq Grade 3 hypertension, subject should be checked the existence or deterioration of proteinuria or other renal damage sign.

(3) Collect blood sample for following tests only for subjects **have 2 vaccinations** in lot-to-lot consistency /immunogenicity group:

- Immune response assessments

(4) Collect blood sample for following tests only for subjects have 3rd vaccination:

- Immune response assessments

- (5) Record adverse events, including AESI, MAAE, SAE, or any symptoms of COVID-19 if any has occurred since the previous visit.

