8.5 Duration of Treatment

The duration of each visit is expected to last between 2 to 3 hours, barring any unexpected adverse reactions.

It takes about 13 months for each subject to participate in the study, from recruiting to the last visit. Some subjects may withdraw the study during the course of the study.

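### V-205 states AESI follow-up through 12 months after the final vaccination, but for subjects who take dose 3 it specifies no contact after Day 365, nominally 123 to 168 days after that dose

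*Supplement*

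**What the plan says.** All references are to protocol V-205.

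- **AESI follow-up.** Section 9.5.6.5 says that AESIs include the listed potential immune-mediated conditions or "any newly identified potential AESI followed through 12 months after" the participant's final vaccination. The same wording is attached to the AE/AESI row of both schedules in section 7.2 (footnote p for the lot-to-lot and immunogenicity group, footnote m for the safety check group) and is repeated in the synopsis.
- **What 12 months means.** The Month 12 visit is defined in the section 7.2 footnotes as "12 months (336 days) after 2nd vaccination".
- **Dose 3.** After unblinding at Visit 5, section 7.1 encourages vaccine recipients to take dose 3 at Visit 6, Day 197 to 242. Section 8.1.9 adds: "The Visit 5 and Visit 6 could be the same day".
- **End of AESI observation.** The primary safety endpoint in section 6.2 is "AESIs and ADEs from Day 1 to Day 365". Section 9.5.5.3 collects AESIs over the study period. The last contact is Day 365 ± 45, where section 8.1.13 asks sites to "Record adverse events, including AESI, MAAE, SAE, or any symptoms of COVID-19". Section 8.5 says: "It takes about 13 months for each subject to participate in the study, from recruiting to the last visit".
- **General statement.** Section 7.1 invites vaccine recipients to an extension study and says: "All subjects who received UB-612 vaccine will be followed up for 12 months". It does not say from which dose the 12 months run.

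**The concern.** Dose 3 was added to a schedule whose last visit is anchored to dose 2. The AESI clause is anchored to the final vaccination, whichever dose that is. For a subject who accepts dose 3 the anchor moves to Day 197 or later, while the end of follow-up stays where it was.

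AESIs are part of the primary safety endpoint. Section 10.5.1 plans a separate summary of AESIs and ADEs after dose 3, and section 9.5.6.5 records that regulators asked for particular vigilance about immune-mediated conditions. A reader who takes the protocol's stated follow-up at face value would credit a low or zero post-booster count with more observation than the schedule gives. Sites, for their part, are given a follow-up period for which no contact is specified.

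The affected group could be large. The adult vaccine arm is about 3850 × 6/7 = 3300 subjects, and all who remain may be offered dose 3. The documents do not give the expected uptake.

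**Working it through.** **Inputs.** Dose 2 at Day 29 (8.1.4). Dose 3 at Day 197 to 242 (7.1, 8.1.9). Visit 5 at Day 197 ± 15, which may coincide with Visit 6 (8.1.8, 8.1.9). Last visit at Day 365 ± 45, so Day 320 to 410 (8.1.13). Twelve months taken as 336 days (7.2).

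**Step 1: reproduce the plan's own figure.** 29 + 336 = 365. The Month 12 visit is exactly 336 days after dose 2, so for two-dose subjects the clause and the schedule agree.

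**Step 2: follow-up after dose 3** (day of last visit minus day of dose 3, and its share of 336 days).

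| Case | Calculation | Days | Share |
|---|---|---|---|
| Nominal, latest dose 3 | 365 − 242 | 123 | 37% |
| Nominal, earliest dose 3 | 365 − 197 | 168 | 50% |
| Window, shortest | 320 − 242 | 78 | 23% |
| Window, longest | 410 − 197 | 213 | 63% |
| Same-day Visit 5/6 at Day 182, last visit at Day 410 | 410 − 182 | 228 | 68% |

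At 30.4375 days per month, 123 and 168 days are 4.0 and 5.5 months. The last row is the most generous combination: it uses the early end of the Visit 5 window (197 − 15 = 182) and the late end of the final window. It is still 336 − 228 = 108 days short.

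**Step 3: what 12 months after dose 3 would need.** 197 + 336 = 533 and 242 + 336 = 578, so a last AESI contact at Day 533 to 578. That is 168 to 213 days beyond Day 365.

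**Step 4: look for a contact that fills the gap.** The contacts after dose 3 are the 7-day call, Visit 7 at 14 days, the calls at Days 253 and 309, and the Day 365 visit. None is later. The 12 months in section 7.1 has no anchor and adds no visit or call. About 13 months of participation matches a screening period of up to 28 days plus 365 days (393 days), with nothing added for dose 3.

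**The case against.** Four points deserve weight.

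1. **The verb may mean case follow-up.** It could be read as following a case once it has been identified. Section 9.5.5.3 continues follow-up of an event until it resolves or stabilises, and section 9.5.6.8 covers serious concerns that reach the investigator later and post-study SUSARs. On that reading there is no gap. It is possible but less natural: a fixed 12-month limit from a vaccination suits a period of ascertainment, whereas case follow-up ends at resolution. These provisions also cover only known or spontaneously reported events. The point therefore rests on the ascertainment reading.

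2. **There may be an extension study.** Section 7.1 names one. A reader might infer that boosted subjects certainly receive no later AESI follow-up. The document does not support that: it supports only that no such contact is specified here. Equally, the dose 3 visits and the Day 365 visit sit inside V-205's own schedule, and no separate extension schedule is shown.

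3. **The endpoint is explicit.** It says Day 365 in sections 6.2 and 10.5.1, and the dose 3 days are stated, so a careful reader can work out the true follow-up. This stands and limits the harm.

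4. **The statistical cost is easily overstated.** Under a constant event rate, a zero-event upper bound on the rate would be 336/168 = 2.0 to 336/123 = 2.7 times the 336-day bound on nominal days, and 336/228 = 1.5 times in the most generous case. This is illustration only. The planned intervals are Clopper-Pearson on proportions, which depend on counts and not on time, and no document supports a constant rate.

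**Conclusion.** The inconsistency is real, and it sits in the protocol's statement about its own follow-up. Read as ascertainment, AESI follow-up through 12 months after the final vaccination is not provided by any contact that V-205 specifies for subjects who take dose 3. They get nominally 123 to 168 days, 78 to 213 with the Day 365 window, and at most 228, against 336.

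The clause may govern all AESIs or only newly identified potential ones. A reader might infer that it promises 12 months for the whole AESI list, but the sentence does not settle this. The mismatch arises under either scope, so long as ascertainment is meant.

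Two-dose subjects are not affected. The AESI endpoint, its window and the planned intervals are not wrong. The consequence is one of interpretation and site instruction, which makes this a correction that should be made and not a threat to the trial's conclusions.

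**What to change.** Restate section 9.5.6.5, the matching footnotes in section 7.2 and the synopsis, and the unanchored 12 months in section 7.1 (and its synopsis counterpart) as AESI follow-up to Day 365. That is 336 days after dose 2 and nominally about 4 to 5.5 months after dose 3. Say at the same time whether the clause covers all AESIs or only newly identified ones.

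In the post-dose-3 AESI and ADE summary already planned in section 10.5.1, show follow-up time since dose 3 beside the counts and percentages. This can be specified in the SAP, which is not shown. That it is not yet written down is no fault in itself; it is the natural companion to the corrected wording.

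The cost is a wording change and one extra entry in a planned table, with no new visits. The downside is that the stated post-booster follow-up becomes less favourable. If the sponsor prefers to keep the 12 months, it would need at least a safety call 336 days after dose 3 (Day 533 to 578), which extends boosted subjects' participation by 168 to 213 days beyond Day 365.
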